15.3.1.2 IMMUNOGENICITY

15.3.1.2.1 EVALUABLE PARTICIPANTS

Evaluable participants include all SAF participants with at least one sample taken post-baseline (during treatment or follow-up period) that is appropriate for ADA testing with a reportable result (positive, negative, or inconclusive). ADA titers will be determined for ADA-positive samples. Results from the confirmatory assays will be used in tables and figures. All available ADA data will be presented in listings.

15.3.1.2.2 ADA ATTRIBUTES

15.3.1.2.2.1 PRE-EXISTING ADA

Participants with ADA-positive sample at baseline are categorized as participants with preexisting ADA.

Note that participants whose baseline ADA sample is missing or non-reportable but has at least one post-baseline sample will be considered as without pre-existing ADA for the analysis.

15.3.1.2.2.2 TREATMENT-BOOSTED ADA

Participants with pre-existing ADAs and at least a two-titer step increase in level of ADA titers at any timepoint after first dosing of study Fabrazyme (including follow-up period) are categorized as participants with treatment-boosted ADAs.

15.3.1.2.2.3 TREATMENT-INDUCED ADA

Participants without pre-existing ADA and developed ADA after first dosing of study Fabrazyme (including follow-up period) are categorized as participants with treatment-induced ADAs.

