5.1 Inclusion Criteria

Participants are eligible to be included in the study only if all the following criteria apply:

- 1. Participants with confirmed diagnosis of FD who are ≥2 and ≤65 years of age at the time of signing the informed consent form (ICF) or assent, if applicable.
 - a. Cohort 1: female participants with body weight ≥30 kg who have been treated with Fabrazyme for at least 3 months without IARs during the most recent 3 infusions.
 - b. Cohort 2: non-classic male participants with body weight ≥30 kg who have been treated with Fabrazyme for at least 3 months without IARs during the most recent 3 infusions.
 - c. Cohort 3: classic male participants with body weight ≥30 kg who have been treated with Fabrazyme for at least 3 months without IARs during the most recent 3 infusions.
 - d. Cohort 4: participants with body weight <30 kg who have been treated with Fabrazyme for at least 3 months without IARs during the most recent 3 infusions.

Note: Classic FD is defined by α GAL level in dried blood spot or leukocyte below 3% of normal value.

2. Women of childbearing potential must use a highly effective method of contraception through the study (refer to Appendix 4 in Section 10.4).

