15.3.1.2.4 ADA RESPONSE VARIABLE

ADA Incidence is defined as the proportion of evaluable participants found to have seroconverted (treatment-induced ADAs) or boosted their pre-existing ADA response (treatment-boosted ADAs) at any timepoint during the study period.

• ADA incidence (%) = 100* (number of treatment-boosted ADA participants + treatment-induced ADA participants)/ total number of evaluable participants

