15.3.1.2.5 ANALYSIS OF IMMUNOGENICITY

During the study treatment period, only results from the samples taken prior to an infusion of the study drug will be considered. During the post treatment period, all samples will be considered.

Document: \\ieedc

Author:

vnasc01\BIOSdata\Sanofi\Fabrazyme\IAB16602\Biostatistics\Documentation\SAP\SAP\Sanofi\Final

Version\lps17726-16-1-9-sap.docx

Version Number: Final V1.0

Version Date: 22Oct2024

Template No.: CS_TP_BS016 Revision 7 Reference: CS_WI_BS005

Effective Date: 01Nov2021

PROTOCOL LPS17726

Analysis Plan Template

Page 51 of 65

If time is not available and it cannot be determined the assessment was prior to the infusion, then the result will be considered missing.

Summary tables for cohorts 1-4 pooled on the SAF analysis set will present:

- Evaluable participants (n)
- Participants with pre-existing ADA (n, %[†])
 - Number of participants with treatment-boosted ADA (n, %[†]) and ADA peak titer (median, min, max)*
- Participants who are ADA negative at baseline $(n, \%^{\dagger})$
 - Number of participants with treatment-induced ADA (n, %[†]) and ADA peak titer (median, min, max)*
 - o Participants with persistent ADA response (n, %[†])
 - o Participants with transient ADA response (n, %[†])
 - o Participants with indeterminate ADA response (n, %[†])
- ADA incidence (%[†])

* ADA peak titer is defined as the highest titer after the first study infusion of Fabrazyme. In case of sparse treatment-boosted or treatment-induced ADA participants (eg, less than 5 participants), ADA peak titer may not be summarized.

Additionally, a summary table of ADA titers per visit will be presented with the following statistics: number, median, Q1, Q3, min, max, and geometric mean along with geometric SD (in case of sparse ADA positive participants, eg, less than 5 participants per visit, the ADA titer may not be descriptively summarized).

Individual ADA titers and median value for the cohorts over time will be presented in a spaghetti

Document: \\ieedc

 $vnasc01\\BIOSdata\\Sanofi\\Fabrazyme\\IAB16602\\Biostatistics\\Documentation\\SAP\\SAP\\Sanofi\\Finally and the properties of th$

Version\lps17726-16-1-9-sap.docx

Author: Version Number: Final V1.0

Version Date: 22Oct2024

Template No.: CS_TP_BS016 Revision 7 Reference: CS_WI_BS005

Effective Date: 01Nov2021

[†] The number of evaluable participants will be the denominator for the percentages.

PROTOCOL LPS17726

Analysis Plan Template

Page 52 of 65

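### Scoring a missing baseline ADA result as no pre-existing ADA can report long-standing antibodies as treatment-induced in participants who have all had Fabrazyme before

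*SAP*

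**What the plan says.** - **Baseline rule (SAP 15.3.1.2.2.1).** A participant with no usable baseline ADA result and at least one post-baseline sample "will be considered as without pre-existing ADA for the analysis".
- **Induced (SAP 15.3.1.2.2.3).** "Participants without pre-existing ADA and developed ADA after first dosing of study Fabrazyme" are treatment-induced.
- **Boosted (SAP 15.3.1.2.2.2).** "Participants with pre-existing ADAs and at least a two-titer step increase in level of ADA titers" are treatment-boosted.
- **Incidence (SAP 15.3.1.2.4).** The numerator adds the "number of treatment-boosted ADA participants" and the number who are treatment-induced. The denominator is all evaluable participants. Under SAP 15.3.1.2.1, being evaluable requires a reportable post-baseline sample but no baseline result.
- **Summary table (SAP 15.3.1.2.5).** Treatment-induced ADA and the persistent, transient and indeterminate classes sit under the row "Participants who are ADA negative at baseline". The footnote reads: "The number of evaluable participants will be the denominator for the percentages".
- **Kinetics (SAP 15.3.1.2.3).** Boosted cases are excluded. An induced response is persistent if the first and last positive timepoints are at least 16 weeks apart.
- **Population (Protocol 5.1).** Every cohort consists of participants "who have been treated with Fabrazyme for at least 3 months without IARs during the most recent 3 infusions".
- **Sampling (Protocol 1.3, Table 1).** ADA blood is drawn from Day 1 onward, before the infusion. There is no ADA sample at screening.

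**The concern.** The rule turns an unknown into an observed negative. In a treatment-naive population that default might be defensible, but nobody here is naive: all four cohorts have prior exposure to the same enzyme, and Protocol Appendix 6 records that the treatment-naive cohort was removed. A positive sample after a missing baseline may therefore be an antibody that was there before the first study infusion.

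The exploratory objective in Protocol Section 3 asks whether a faster infusion rate influences immunogenicity. A participant with a flat, long-standing titer and no Day 1 result could be reported as having seroconverted on the faster infusions, with a persistent response. Day 1 is the only scheduled baseline sample, so one lost or unreportable tube is enough. No sensitivity analysis and no row for unknown baseline status is planned. SAP 3.3 drops confidence intervals and by-cohort summaries, so the pooled table would carry no sign of the problem.

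The rule also sits oddly beside SAP 7.3.1.3.1, which does not impute missing ADA titers.

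**Working it through.** The plan states no expected ADA rate, no expected rate of missing baselines and no sample size calculation, so it has no figure to reproduce. The check applies the SAP's own definitions.

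**Step 1. What happens to a participant with a missing baseline.**

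| True status before the study | On study | SAP class | Effect on ADA incidence |
|---|---|---|---|
| Positive | Positive, not boosted | Induced | Overstated by one participant |
| Positive | Boosted | Induced instead of boosted | None, since incidence sums both; the case wrongly enters kinetics |
| Negative | Becomes positive | Induced | Correct |
| Any | Negative throughout | Not induced | Counts in the denominator only |

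The rule can leave incidence right or too high. It cannot make it too low.

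**Step 2. Size of one misclassification.** SAP 15.3.1.2.4 gives incidence = 100 × (boosted + induced) / evaluable. SAP 3.1 gives at most 14 participants; assume all 14 are evaluable. One participant is 100 × 1/14 = 7.1 points.

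Let k be the number with a missing baseline who were truly positive and not boosted, and b the number of true boosted or induced cases. The SAP rule gives 100 × (b + k)/14. Leaving the k participants out gives 100 × b/(14 − k).

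| b | k | SAP rule | Unknown baselines left out |
|---|---|---|---|
| 0 | 1 | 1/14 = 7.1% | 0/13 = 0% |
| 0 | 2 | 2/14 = 14.3% | 0/12 = 0% |
| 0 | 3 | 3/14 = 21.4% | 0/11 = 0% |
| 1 | 1 | 2/14 = 14.3% | 1/13 = 7.7% |
| 1 | 2 | 3/14 = 21.4% | 1/12 = 8.3% |
| 1 | 3 | 4/14 = 28.6% | 1/11 = 9.1% |

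**Step 3. Kinetics.** Protocol Table 1, footnote c, says Visits 3, 8 and 11 should take place for everyone. The target days in SAP 6.6.1 are 14, 84 and 196. Week 2 to Week 28 is (196 − 14)/7 = 26 weeks, and Week 12 to Week 28 is (196 − 84)/7 = 16 weeks. A participant who was positive all along and has no baseline result meets the 16-week criterion and is labelled a persistent treatment-induced response, even if the titer never moved.

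**Step 4. How often.** The documents do not say, so this is an assumption with a range. Suppose each baseline is missing with probability m, each participant has pre-existing ADA with probability p, the two are independent, and antibodies present before the study are still detected on study. The expected number affected is 14mp, and the chance of at least one is 1 − (1 − mp)^14.

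| m | p | Expected | Chance of at least one |
|---|---|---|---|
| 5% | 30% | 0.21 | 19% |
| 10% | 50% | 0.70 | 51% |
| 20% | 90% | 2.52 | 94% |

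These counts include any who were boosted, for whom the label is wrong but incidence is not. With m = 0 the effect is zero.

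**Step 5. Does an untimed Day 1 sample count as baseline?** SAP 6.3 accepts a measurement that coincides with the first dose if it was planned before dosing, and Protocol Table 1 plans this one before the infusion. SAP 15.3.1.2.5 sets a sample to missing if its time is not available and it cannot be shown to precede the infusion. The two sections point in different directions, and neither refers to the other.

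**The case against.** The strongest reply is that this is a small matter. The incidence and kinetics categories are exploratory and descriptive, and SAP 3.3 shows that the SAP added them. The protocol's own ADA endpoint is change in titer (Protocol Section 3 and 9.3.4). SAP 7.3.1.3.1 imputes no missing titers, and the by-visit titer summary does not use the pre-existing or induced split. All ADA data are listed by participant and visit and individual titers are plotted, so with 14 people a flat titer beside a blank Day 1 can be found. All of this stands. It limits the consequence but does not make the rule right.

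A second reply concerns the remedy. Removing these participants from every count would lose information: someone with no Day 1 result, a negative Week 2 and a positive Week 12 has converted on study. This also stands, and it shapes the fix below.

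Some stronger readings are tempting, but the documents do not support them:

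- **That every missing baseline adds 7.1 points.** It does so only for a participant who was truly positive and not boosted.
- **That the SAP expects fewer than five positives, so one error would be a large share of them.** SAP 15.3.1.2.5 mentions fewer than five only as an example of when peak titers may not be summarized. It forecasts nothing.
- **That the rule certainly applies to untimed Day 1 blood.** SAP 6.3 may rescue that sample, so the point is unresolved.

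**Conclusion.** The concern holds in limited form. The rule for a missing or non-reportable baseline is stated, it is carried through to treatment-induced ADA, ADA incidence and kinetics, and it does not suit a population with at least 3 months of prior exposure. With 14 evaluable participants, each one who was truly positive and not boosted overstates ADA incidence by 7.1 points. Each one who was truly positive and boosted is moved to the wrong class and wrongly enters kinetics.

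The conclusion rests on at least one baseline being missing or non-reportable in a participant with pre-existing ADA that is still detected on study. The documents give no rate for either, so the 19% to 94% range reflects assumed inputs and is not a prediction. A reader might infer that the study's answer on immunogenicity as a whole is biased. The documents do not support that: the titer-change endpoint is untouched, as are the primary and secondary endpoints. Minor in weight, but worth correcting before database lock.

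**What to change.** 1. In SAP 15.3.1.2.2.1, replace the default with a third category, baseline ADA status unknown, and give it its own row in the SAP 15.3.1.2.5 table. Do not place these participants under the baseline-negative row or call them treatment-induced by default.
2. Within that row, allow a documented negative on-study sample followed by a positive one to be reported as on-study conversion.
3. Show ADA incidence and the kinetics classes twice: with these participants handled as the SAP now does, and with them left out of numerator and denominator. Keep them in all listings and titer plots.
4. State in SAP 6.3 or 15.3.1.2.5 which rule governs a Day 1 ADA sample with no recorded time.

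The cost is one extra table row and a second incidence figure with a slightly smaller denominator, plus matching edits to the incidence formula, the table footnote and the kinetics text. No new data are needed. If every baseline is reportable, the new row is empty and the two sets of figures agree.

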15.3.1.2.3 KINETICS OF ADA RESPONSE

Treatment boosted ADAs are excluded from the analysis of ADA kinetics.

Document: \\ieedc

 $vnasc01\\BIOS data\\Sanofi\\Fabrazyme\\IAB16602\\Biostatistics\\Documentation\\SAP\\SAP\\Sanofi\\Finally and the properties of t$

Version\lps17726-16-1-9-sap.docx

Author: Version Number: Final V1.0

Version Date: 22Oct2024

Template No.: CS_TP_BS016 Revision 7 Reference: CS_WI_BS005

Effective Date: 01Nov2021

PROTOCOL LPS17726

Analysis Plan Template

Page 50 of 65

15.3.1.2.3.1 PERSISTENT ADA RESPONSE

Persistent ADA response is defined as treatment-induced ADA detected at two or more timepoints post-baseline (including follow-up period), where the first and last ADA-positive timepoints (irrespective of any negative samples in between) are separated by at least 16 weeks.

15.3.1.2.3.2 TRANSIENT ADA RESPONSE

Transient ADA response is defined as treatment-induced ADA detected at only one timepoint post baseline (excluding the last sampling timepoint) or at two or more timepoints post-baseline (including the follow-up period), where the first and last ADA-positive timepoints (irrespective of any negative samples in between) are separated by less than 16 weeks and the participant's last timepoint is ADA-negative.

15.3.1.2.3.3 INTERMEDIATE ADA RESPONSE

Indeterminate ADA response is defined as when only the last timepoint is ADA-positive and all previous samples are ADA-negative or the last two samples (including follow-up period), separated by less than 16 weeks are positive.

15.3.1.2.4 ADA RESPONSE VARIABLE

ADA Incidence is defined as the proportion of evaluable participants found to have seroconverted (treatment-induced ADAs) or boosted their pre-existing ADA response (treatment-boosted ADAs) at any timepoint during the study period.

• ADA incidence (%) = 100* (number of treatment-boosted ADA participants + treatment-induced ADA participants)/ total number of evaluable participants

15.3.1.2.5 ANALYSIS OF IMMUNOGENICITY

During the study treatment period, only results from the samples taken prior to an infusion of the study drug will be considered. During the post treatment period, all samples will be considered.

Document: \\ieedc

Author:

vnasc01\BIOSdata\Sanofi\Fabrazyme\IAB16602\Biostatistics\Documentation\SAP\SAP\Sanofi\Final

Version\lps17726-16-1-9-sap.docx

Version Number: Final V1.0

Version Date: 22Oct2024

Template No.: CS_TP_BS016 Revision 7 Reference: CS_WI_BS005

Effective Date: 01Nov2021

PROTOCOL LPS17726

Analysis Plan Template

Page 51 of 65

If time is not available and it cannot be determined the assessment was prior to the infusion, then the result will be considered missing.

Summary tables for cohorts 1-4 pooled on the SAF analysis set will present:

- Evaluable participants (n)
- Participants with pre-existing ADA (n, %[†])
 - Number of participants with treatment-boosted ADA (n, %[†]) and ADA peak titer (median, min, max)*
- Participants who are ADA negative at baseline $(n, \%^{\dagger})$
 - Number of participants with treatment-induced ADA (n, %[†]) and ADA peak titer (median, min, max)*
 - o Participants with persistent ADA response (n, %[†])
 - o Participants with transient ADA response (n, %[†])
 - o Participants with indeterminate ADA response (n, %[†])
- ADA incidence (%[†])

* ADA peak titer is defined as the highest titer after the first study infusion of Fabrazyme. In case of sparse treatment-boosted or treatment-induced ADA participants (eg, less than 5 participants), ADA peak titer may not be summarized.

Additionally, a summary table of ADA titers per visit will be presented with the following statistics: number, median, Q1, Q3, min, max, and geometric mean along with geometric SD (in case of sparse ADA positive participants, eg, less than 5 participants per visit, the ADA titer may not be descriptively summarized).

Individual ADA titers and median value for the cohorts over time will be presented in a spaghetti

Document: \\ieedc

 $vnasc01\\BIOSdata\\Sanofi\\Fabrazyme\\IAB16602\\Biostatistics\\Documentation\\SAP\\SAP\\Sanofi\\Finally and the properties of th$

Version\lps17726-16-1-9-sap.docx

Author: Version Number: Final V1.0

Version Date: 22Oct2024

Template No.: CS_TP_BS016 Revision 7 Reference: CS_WI_BS005

Effective Date: 01Nov2021

[†] The number of evaluable participants will be the denominator for the percentages.

PROTOCOL LPS17726

Analysis Plan Template

Page 52 of 65

plot in Safety analysis set.

Listing of participants presenting their ADA status (positive, negative, inconclusive) and ADA titer at each visit will be displayed by cohort in Safety analysis set.

If an ADA titer result is reported as non-numerical, it will be imputed as described in Section 7.3.1.3.1 for summary tables and figures. The listing will present the results as reported.

15.3.2 Intercurrent Event Handling and Data Imputation for Exploratory Variable(s)

Refer to Sections 7.2 and 7.3.1.3.1 for details about intercurrent events and management of missing data.

16 SAFETY OUTCOMES

16.1 ADVERSE EVENTS

Adverse Events (AEs) will be coded to a preferred term (PT) and associated primary system organ class (SOC) using Medical Dictionary for Regulatory Activities (MedDRA) central coding dictionary, Version 27.0 or above depending on the version in effect at IQVIA at time of database lock. The information on AEs are captured in eCRF pages: Adverse Events, Adverse Event of Special Interest and Adverse Events of Special Interest-Infusion Associated Reaction. AEs that worsened or became serious are recorded as new records in the eCRF, and as such are counted as separate events for analysis. "Start date (and time)" below refer to the start date (and time) of each AE record.

The AEs will be analyzed in the following 3 categories:

- Pre-treatment AEs: AEs with start date (and time) < first dose of Fabrazyme start date/time.
- Treatment-emergent adverse events (TEAEs): AEs with start date (and time) ≥ first dose of Fabrazyme start date/time and <= last dose of study Fabrazyme end date. AEs will be

Document: \\ieedc

Author:

 $vnasc01\BIOS data\Sanofi\Final\Version\Pinal\Version\Pinal\Final\Version\Pinal\Final\Version\Pinal\F$

Version(lps 17 / 20-10-1-9-5ap.docx

Version Number: Final V1.0

Version Date: 22Oct2024

Template No.: CS_TP_BS016 Revision 7 Reference: CS_WI_BS005

Effective Date: 01Nov2021

PROTOCOL LPS17726

Analysis Plan Template

Page 53 of 65

classified as TEAEs in the case where it's not possible to determine whether they're treatment emergent, refer to Appendix 20.1 - 'Algorithm for Treatment Emergent Adverse Events'.

• Post-treatment AEs: AEs with start date > last dose of study Fabrazyme end date.

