	Treatment : Fabrazyme 1 mg/kg Q2W up to the rate tolerated (refer to Section 6.2), with oral premedications given 30 minutes prior to each infusion.
	Endpoint : Binary, calculated separately for each infusion duration: Participant achieved infusion duration without experiencing any IAR.
	Intercurrent events: A while-on-treatment approach will be applied. Participants never observed to tolerate any infusion rate will be counted as not achieving the required duration for the infusion. A treatment policy approach will be applied in case pre-medications are not given as described within the protocol. No action will be taken for this event for the analysis even when pre-medications are not given as described within the protocol.
	Summary measure : For each infusion duration, number and % of participants achieving the endpoint.

Objectives	Estimand Description/Endpoints	
	Population : Participants with confirmed diagnosis of FD, age 2 to 65 years, Fabrazyme-experienced, treated for at least 3 months without IARs during the most recent 3 infusions.	
	Treatment : Fabrazyme 1 mg/kg Q2W up to the rate tolerated (refer to Section 6.2), with oral premedications given 30 minutes prior to each infusion.	
	Endpoint : Binary, calculated separately for each infusion duration: Participant achieved infusion duration without experiencing a second IAR.	
	Intercurrent events: A while-on-treatment approach will be applied. Participants never observed to tolerate any infusion rate will be counted as not achieving the required duration for the infusion. A treatment policy approach will be applied in case pre-medications are not given as described within the protocol. No action will be taken for this event for the analysis even when pre-medications are not given as described within the protocol.	
	Summary measure: For each infusion duration, number and % of participants achieving the endpoint.	
Exploratory		
To investigate the influence of increased infusion rate on the immunogenicity and efficacy of	Changes of plasma lyso-GL3 from baseline to 6 months follow-up	
Fabrazyme treatment	Change of the titer of ADA to Fabrazyme over 6 months follow-up	
Safety		
To investigate the influence of increased infusion rate on the safety of Fabrazyme treatment	Number, severity, and nature of AEs including IARs	

Abbreviations: ADA = anti-drug antibody, AE = adverse event; FD = Fabry disease; IAR = infusion associated reaction; lyso-GL3 = globotriaosylsphingosine; Q2W = every 2 weeks.

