- Alternative causes, such as underlying disease(s), concomitant therapy, and other risk factors, as well as the temporal relationship of the event to study intervention administration, will be considered and investigated.
- For causality assessments, events assessed as having a reasonable possibility of being related to study intervention will be considered "related." Events assessed as having no reasonable possibility of being related to study intervention will be considered "unrelated."
- The Investigator will also consult the product prescribing information, for marketed products, in his/her assessment.
- For each AE/SAE, the Investigator **must** document in the medical notes that he/she has reviewed the AE/SAE and has provided an assessment of causality.
- There may be situations in which an SAE has occurred, and the Investigator has minimal information to include in the initial report to the Sponsor or designee. However, it is very important that the Investigator always makes an assessment of causality for every event before the initial transmission of the SAE data to the Sponsor or designee.
- The Investigator may change his/her opinion of causality in light of follow-up information and send an SAE follow-up report with the updated causality assessment.
- The causality assessment is one of the criteria used when determining regulatory reporting requirements.

Follow-up of AEs and SAEs

- The Investigator is obligated to perform or arrange for the conduct of supplemental
 measurements and/or evaluations as medically indicated or as requested by the Sponsor or
 designee to elucidate the nature and/or causality of the AE or SAE as fully as possible. This
 may include additional laboratory tests or investigations, histopathological examinations, or
 consultation with other health care professionals.
- If a participant dies during participation in the study or during a recognized follow-up period, the Investigator will provide the Sponsor or designee with a copy of any postmortem findings including histopathology.
- New or updated information will be recorded in the originally submitted documents.
- The Investigator will submit any updated SAE data to the Sponsor or designee within 24 hours of the Investigator's awareness of the information.

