16.1.7 ADVERSE EVENTS OF SPECIAL INTEREST

16.1.7.1 Infusion Associated Reaction

In this study, IAR is defined as AEs the Investigator considers related to Fabrazyme infusion, occurring on same day as infusion and only after infusion has begun. Each individual AE occurrence will be considered separate when analyzing Adverse Events.

IARs are events recorded as Adverse Event of Special Interest (Infusion Associated Reaction) on the Adverse Events page of the eCRF.

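### SAP 16.1 treats each worsening as an unlinked event with its own date, so the severe or serious part of a last-infusion reaction can become post-treatment, and AE-table totals count records rather than reactions

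*SAP*

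**What the plan says.** The safety endpoint in Protocol 3.0 is "Number, severity, and nature of AEs including IARs", so both counts and severity belong to it.

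SAP 16.1 sets the rules for AE records:
- Splitting: "AEs that worsened or became serious are recorded as new records in the eCRF, and as such are counted as separate events for analysis".
- Dating: the start dates used for classification "below refer to the start date (and time) of each AE record".
- Cut-off: "Post-treatment AEs: AEs with start date > last dose of study Fabrazyme end date". SAP 6.1 likewise ends the treatment-emergent period on the date of the last dose. Protocol 9.3.1 defines that period as running from first dose to last dose plus follow-up.

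SAP 16.1.7.1 adds the rules for IARs:
- An IAR is an event "occurring on same day as infusion and only after infusion has begun".
- In the data, "IARs are events recorded as Adverse Event of Special Interest (Infusion Associated Reaction) on the Adverse Events page of the eCRF".
- For the AE tables, "Each individual AE occurrence will be considered separate when analyzing Adverse Events".

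Protocol 8.5.6, and SAP 15.1.4 and 15.2.3 for the primary and secondary endpoints, count one IAR per infusion however many times it shows itself.

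SAP 16.1.8 reports total events beside participant counts. Intensity is tabulated for TEAEs only, taking the worst grade per participant within SOC and PT (SAP 16.1.1). Post-treatment AEs get a SOC/PT table and a listing, with no breakdown by intensity or seriousness.

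**The concern.** A reaction that evolves is one clinical event, but the SAP turns it into several unrelated ones. The most serious effect is at the last infusion. If the reaction starts that day and becomes severe or serious later, the later record falls past the cut-off, although the reaction itself began on treatment.

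The last infusion is where reactions matter most in this study:
- A second IAR stops treatment (Protocol 4.5, 6.2, 7.1), so the infusion that caused it is the last one.
- A significant AE or SAE can lead to withdrawal (Protocol 7.1). A reaction that turns serious the next day can therefore itself make the infusion the last.
- Reaching the shortest planned duration ends treatment. This route is narrower, because success requires no IAR. It leaves a same-day event not entered as an IAR, or one starting after the infusion ended, since Protocol 6.2 words tolerance as no IAR seen during the infusion.

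The lesser effect is on totals. The AE tables and the endpoint sections can report different numbers of IARs for the same reaction.

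**Working it through.** The plan gives no figure to reproduce: it has no hypothesis, event target or sample-size calculation. The check applies the SAP rules to one invented reaction with three records: mild, then moderate, then severe and serious.

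**Rules used**
- Event total = number of records (SAP 16.1, 16.1.8).
- TEAE if first dose ≤ record start ≤ last dose date; post-treatment if record start > last dose date (SAP 16.1).
- Meets the IAR time condition if record start day = infusion day (SAP 16.1.7.1).
- IARs for the primary and secondary endpoints = number of distinct infusions with an IAR (SAP 15.1.4, 15.2.3).

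**Inputs** (assumed): infusions on Days 1, 15, 29, 43 and 57.
- Case A: all three records on Day 29.
- Case B: two records on Day 29, the severe and serious one on Day 30.
- Case C: two records on Day 57 (the last infusion), the severe and serious one on Day 58.

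| Result | A | B | C |
|---|---|---|---|
| Records counted as events | 3 | 3 | 3 |
| TEAEs | 3 | 3 | 2 |
| Post-treatment AEs | 0 | 0 | 1 |
| Records meeting the same-day IAR condition | 3 | 2 | 2 |
| Worst TEAE intensity | severe | severe | moderate |
| Treatment-emergent serious records | 1 of 1 | 1 of 1 | 0 of 1 |
| Participants with an IAR | 1 | 1 | 1 |
| IARs for primary and secondary endpoints | 1 | 1 | 1 |

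**Reading the table**
1. In C, Day 58 > Day 57, so the severe and serious record is post-treatment. The worst-grade rule in SAP 16.1.1 cannot recover it, because the intensity table is built from TEAEs. With all 14 participants treated, the severe-TEAE and treatment-emergent SAE rows each read 0 where the reaction would give 1/14 = 7.1%.
2. The split can also change causality. If relationship is missing, SAP 7.3.2.2.2 assigns related to a TEAE but not related to a post-treatment AE.
3. Under the Protocol 9.3.1 period, which includes follow-up, the Day 58 record would stay treatment-emergent. The legible entries in SAP Table B (changes from protocol) do not mention the shorter period.
4. In A, one reaction in one infusion is 3 IAR events in the AE tables and 1 IAR in the endpoint analyses.
5. In B, the TEAE intensity table still shows severe, and only the IAR label of the third record is uncertain.

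**The case against.** **The new-record convention is pre-specified and has a use.** It preserves the date on which an event became severe or serious. That stands, but it does not require leaving the records unlinked.

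**The cause of case C is the cut-off, not the splitting.** Restoring the protocol's period would keep the late record treatment-emergent without any linking. This is partly right, and the two definitions should be reconciled. Linking is still needed for the event totals and for the IAR status of later records, and it gives the same answer in case C under either period.

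**Nothing is lost.** Every record appears in a by-cohort listing, and readers can follow 14 participants by eye. That is true, but the serious record sits in the post-treatment listing, away from the treatment-emergent SAE listing, and the summary tables are wrong for it.

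A reader might infer more than the documents support:
- *That a next-day worsening automatically stops being an IAR.* IARs are identified by the eCRF entry, not derived from dates. The label is lost only if the site does not flag the later record, and the participant keeps an IAR through the first record.
- *That an IAR table will show grades that are too mild.* No table of IARs by intensity or seriousness is planned.
- *That Protocol 10.3.3 forbids new records.* Its sentence, "New or updated information will be recorded in the originally submitted documents", stands among the follow-up duties for AEs and SAEs. It does not say whether a change of grade opens a new eCRF record.
- *That totals are inflated by a known percentage.* The documents give no rate of worsening, so any figure would only restate an assumption.

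**Conclusion.** The point holds in two parts. First, the severe or serious part of a reaction that began on the last infusion day can drop out of the treatment-emergent summaries. In the worked case this changes 1 treatment-emergent serious event to 0 and lowers the worst TEAE grade from severe to moderate. It requires a worsening dated on a later calendar day and no further study infusion. How often that will happen cannot be estimated from the documents, but with at most 14 participants a single case changes the safety picture.

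Second, AE-table event totals are record counts, so they do not match the one-IAR-per-infusion rule used elsewhere. This multiple counting leaves participant percentages and the primary and secondary endpoints unchanged. The participant rows for severe TEAEs and treatment-emergent SAEs are affected only through the first part.

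The study is descriptive, so no test is distorted. The rule should still be changed, because it gives a wrong result on the safety endpoint and is cheap to correct.

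**What to change.** In SAP 16.1 and 16.1.8:
1. Link each worsened or newly serious record to its parent AE, carry the parent's treatment-emergent and IAR status to it, and summarise the episode at its highest intensity and seriousness.
2. Keep the new-record rule for conditions present before the first infusion that worsen on treatment. Those are correctly new TEAEs.
3. Report an infusion-level IAR count with maximum severity beside the existing totals, and label those totals as record counts.
4. Reconcile the treatment-emergent period in SAP 6.1 and 16.1 with Protocol 9.3.1, and list any deliberate difference in SAP 3.3.

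Listings can stay as planned. The cost is SAP wording, some programming, and manual review of links for at most 14 participants. Linking involves some judgement, so it should be settled before database lock.
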